### 3.1.2 Treatment Regimen

CCI

- Group 1: MEDI3506 30 mg (0.2 mL), n = 95
- Group 2: MEDI3506 60 mg (0.4 mL), n = 95
- Group 3: MEDI3506 120 mg (0.8 mL), n = 95
- Group 4: MEDI3506 300 mg (2 mL), n = 140
- Group 5: Placebo (0.2 mL), n = 32
- Group 6: Placebo (0.4 mL), n = 32
- Group 7: Placebo (0.8 mL), n = 32
- Group 8: Placebo (2 mL), n = 44

All subjects will also receive daily oral tablets of 10 mg dapagliflozin starting on Day 85 until Day 168. Subjects already taking an SGLT2i will be rolled over to 10 mg dapagliflozin.

Dapagliflozin should be taken in the morning with or without food.

### 3.1.3 Study Conduct Mitigation During Study Disruptions Due to Cases of Civil Crisis, Natural Disaster, or Public Health Crisis

The guidance given below supersedes instructions provided elsewhere in this protocol and should be implemented only during cases of civil crisis, natural disaster, or public health crisis (eg, during quarantines and resulting site closures, regional travel restrictions, and considerations if site personnel or study subjects become infected with SARS-CoV-2 or similar pandemic infection) which would prevent the conduct of study-related activities at study sites, thereby compromising the study site staff or the subject's ability to conduct the study. The investigator or designee should contact the study sponsor to discuss whether the mitigation plans below should be implemented.

To ensure continuity of the clinical study during a civil crisis, natural disaster, or public health crisis, changes may be implemented to ensure the safety of study subjects, maintain compliance with Good Clinical Practice, and minimize risks to study integrity.

Where allowable by local health authorities, ethics committees, healthcare provider guidelines (eg, hospital policies) or local government, these changes may include the following options:

- Obtaining consent for the mitigation procedures (note, in the case of verbal consent, informed consent form (ICF) should be signed at the subject's next contact with the study site).

- Rescreening: Additional rescreening for screen failure and to confirm eligibility to participate in the clinical study can be performed in previously screened subjects. The investigator should confirm this with the designated Study Physician.
- Home or Remote visit (when applicable): Performed by a site qualified Healthcare Professional (HCP) or HCP provided by a third-party vendor (TPV).
- Telemedicine visit: Remote contact with the subjects using telecommunications technology including phone calls, virtual or video visits, and mobile health devices.

For further details on study conduct during civil crisis, natural disaster, or public health crisis, refer to Appendix G.

## 3.2 Rationale for Dose, Population, and Endpoints

### 3.2.1 Dose Rationale

CCI

A once daily dose of 10 mg dapagliflozin has been established as having favorable tolerability and effect on albuminuria in DKD (Heerspink et al, 2020a).

### 3.2.2 Rationale for Study Population

Studying subjects with DKD enables assessment of the clinical efficacy and safety of MEDI3506, as well as supporting dose selection, in a population at risk for progression to renal failure on top of standard of care, including ACEi or ARB and SGLT2i (Go et al, 2018). Subjects with DKD with eGFR 25-75 mL/min/1.73 m^2 will be recruited, as clinical studies support that the inflammatory process driving CKD progression is increased in subjects with reduced eGFR (Alicic et al, 2018; Perlman et al, 2015; Tuttle et al, 2018).

### 3.2.3 Rationale for Endpoints

The primary endpoint in this study is the change in UACR from baseline. The change in urine albumin excretion during the treatment period provides information about renal efficacy, and a sustained effect following investigational drug washout suggests benefit to renal structure.

The evaluation of MEDI3506/placebo taken with ACEi or ARB, or with ACEi or ARB plus dapagliflozin will clarify the interaction with standard care. The treatment duration allows a suitable assessment of safety and immunogenicity following multiple dose administration and is of sufficient length to evaluate effects on urine albumin excretion (Heerspink et al, 2019).

Standard measures of PK analysis will be used to inform understanding of MEDI3506 and dapagliflozin PK in subjects with DKD as well as help to inform the exposure-response relationship. Standard safety and immunogenicity measures will be assessed.

CCI

## 4 MATERIALS AND METHODS

### 4.1 Subjects

#### 4.1.1 Number of Subjects

Approximately 565 subjects are planned to be randomized in this study into 8 treatment groups (Section 3.1.2).

#### 4.1.2 Inclusion Criteria

Subjects must meet all of the following criteria:

- 1 Adult men or women  $\geq 18$  years of age at Visit 1.
- 2 Written informed consent and any locally required authorization (eg, data privacy) obtained from the subject prior to performing any protocol-related procedures, including screening evaluations.
- 3 DKD defined as
  - (a) diagnosis of T2DM and
  - (b) eGFR 25-75 mL/min/1.73 m^2 based on Chronic Kidney Disease Epidemiology Collaboration (CKD-EPI) equation a and
  - (c) UACR defined as 100-3000 mg albumin/g creatinine based on the mean of 3 sequential first morning void midstream urine samples at Visit 2.
- 4 BP  $\leq 150/100$  mmHg at Visit 1 and Visit 3.
- 5 Stable dose of ACEi or ARB for at least 6 weeks prior to Visit 1 and throughout the screening period with ACEi and ARB dosing according to local guidelines. Subjects who have been deemed unable to tolerate ACEi or ARB therapy due to allergy or complications may be enrolled. Minor dose adjustment within 2 weeks before Visit 1 is acceptable (see Section 4.7.2).

- 6 For subjects on any additional antihypertensive medication (including diuretic therapy), doses must be stable for at least 6 weeks prior to Visit 1 and throughout the screening period.
- 7 For subjects on SGLT2i treatment prior to enrollment, doses must be stable for at least 4 weeks prior to Visit 3. Existing SGLT2i treatment will be stopped and switched to 10 mg dapagliflozin on Day 85.
- 8 Up-to-date influenza and pneumococcal pneumonia vaccinations (subject-reported) according to local recommendations, at least 28 days prior to Visit 3 OR confirmation of off-season intent to get vaccinated. Patients screened outside of the influenza season (including those who were not vaccinated in the previous season) are eligible for randomization provided that the vaccination is planned once the influenza vaccine for the next season becomes available. For such patients, investigators are asked to confirm the patient's intent to get vaccinated for the next season. Patients who do not plan to get vaccinated against influenza should not be randomized.
- 9 Contraceptive use by men or women should be consistent with local regulations regarding the methods of contraception for those participating in clinical studies.
  - (a) Male subjects:
    - For genotoxic investigational products, the male subject should use condom during treatment and until the end of relevant systemic exposure in the male subject, plus a further 90-day period (until 24 weeks after the last dose of study intervention (MEDI3506). For a non-pregnant women of childbearing potential (WOCBP) partner, contraception recommendations should also be considered.
  - (b) Female subjects:
    - Women not of childbearing potential are defined as women who are either permanently sterilized (hysterectomy, bilateral oophorectomy, or bilateral salpingectomy), or who are postmenopausal. Women will be considered postmenopausal if they have been amenorrhoeic for 12 months prior to the planned date of Visit 3 without an alternative medical cause. The following age-specific requirements apply:
      - Women < 50 years old would be considered postmenopausal if they have been amenorrhoeic for 12 months or more following cessation of exogenous hormonal treatment and follicle-stimulating hormone levels in the postmenopausal range.
      - Women  $\geq$  50 years old would be considered postmenopausal if they have been amenorrhoeic for 12 months or more following cessation of all exogenous hormonal treatment.
    - Female subjects of childbearing potential must use one highly effective form of birth control. A highly effective method of contraception is defined as one that can achieve a failure rate of less than 1% per year when used consistently and correctly. Women of childbearing potential who are sexually active with a non-sterilized male partner must agree to use one highly effective method of birth control, as defined below, from enrollment throughout the study and until at least 12 weeks after last dose of study intervention (MEDI3506). Cessation of contraception after this point should be discussed with a responsible physician.

Periodic abstinence (calendar, symptothermal, post-ovulation methods), withdrawal (coitus interruptus), spermicides only, and lactational amenorrhea method are not acceptable methods of contraception. Female condom and male condom should not be used together. All WOCBP must have a negative serum pregnancy test result at Visit 1.

- Highly effective birth control methods include: sexual abstinence (periodic abstinence eg, calendar, ovulation, symptothermal, post-ovulation methods), declaration of abstinence for the duration of exposure to investigational product [MEDI3506], and withdrawal are not acceptable methods of contraception], a vasectomized partner, Implanon®, bilateral tubal occlusion, intrauterine device/levonorgestrel intrauterine system, Depo-Provera™ injections, oral contraceptive, and Evra Patch™, Xulane™, or NuvaRing®. Women of childbearing potential must agree to use one highly effective methods of birth control, as defined above, from enrollment throughout the study up to the end of the follow-up period at Visit 10.

10 Able and willing to comply with the requirements of the protocol and complete the study.

a CKD-EPI equation:  $eGFR = 141 \times \min(Scr/\kappa, 1)^a \times \max(Scr/\kappa, 1)^{-1.209} \times 0.993^{Age} \times 1.018$  [if female]  $\times 1.159$  [if black] (Levey et al, 2009). For subjects with amputation, eGFR will be adjusted based on estimated body weight loss.

#### 4.1.3 Exclusion Criteria

Any of the following would exclude the subject from participation in the study:

- 1 Concurrent enrollment in another clinical study involving an investigational treatment or drug, or received administration of an investigational drug or participation in a device trial within 3 months prior to Visit 1.
- 2 Previous participation in a MEDI3506 clinical trial.
- 3 Diagnosis of CKD other than diabetic renal disease (hypertensive nephrosclerosis superimposed on DKD is acceptable).
- 4 Serum potassium > 5.5 mmol/L at Visit 1 that cannot be adjusted to values  $\leq 5.5$  mmol/L by appropriate management (Appendix E).
- 5 Significant hepatic disease, including, but not limited to, acute hepatitis, chronic active hepatitis, or severe hepatic insufficiency, including subjects with ALT and/or AST > 3  $\times$  ULN and/or TBL > 2 mg/dL (> 34.2  $\mu$ mol/L). Subjects with TBL > 2 mg/dL (> 34.2  $\mu$ mol/L) and documented Gilbert's syndrome will be allowed to participate.
- 6 Hemoglobin (Hb) A1c > 10.5% measured at Visit 1.
- 7 B-type natriuretic peptide (BNP) level > 200 pg/mL at Visit 1.
- 8 History of clinically significant heart disease including but not limited to any of the following:
  - (a) Clinically significant congenital or acquired valvular disease, cardiomyopathy or severe pulmonary hypertension, unstable ischemic heart disease, or recent myocardial infarction < 6 months of Visit 1;

- (b) Left ventricular (LV) ejection fraction < 40%, based on transthoracic echocardiogram performed during Visit 2;
  - (c) New York Heart Association Class 3 or 4 or history of hospitalization for heart failure within the past 12 months prior to Visit 1;
  - (d) History of unstable arrhythmias.
- 9 Any of the following concomitant conditions or diseases at Visit 1:
- (a) History of treated ulcerative colitis, Crohn's disease, or microscopic colitis within the last 3 years;
  - (b) Anticipated dialysis or renal transplantation within 1 year;
  - (c) A history of alcohol and/or substance abuse (including positive drugs of abuse screen at Visit 1) that could interfere with the conduct of the trial;
  - (d) Prior malignancy other than:
    - (i) non-melanoma skin cancer (squamous or basal cell carcinoma) treated for complete cure
    - (ii) cervical cancer in situ treated for complete cure
    - (iii) any other history of malignancy treated with apparent success with curative therapy (response duration of > 5 years);
  - (e) History of underlying condition that predisposes the subject to infections (eg, history of splenectomy, known primary or secondary immune deficiency syndromes, cirrhosis);
  - (f) Infections:
    - (i) Significant infection (viral, bacterial, or fungal) including unexplained diarrhea within 4 weeks prior to Visit 3
    - (ii) History of Herpes zoster with last flare occurring within 3 months of Visit 1
    - (iii) Positive test for or history of treatment for hepatitis B, hepatitis C, or human immunodeficiency virus (HIV). Subjects positive for hepatitis B surface antigen (HBsAg) or antibody to hepatitis B core antigen (anti-HBc) are excluded. Those with a history of hepatitis B vaccination without a history of hepatitis B are permitted to enroll
  - (g) History or evidence of active tuberculosis (TB) infection at Visit 1 or one of the risk factors for tuberculosis such as but not limited or exclusive to:
    - (i) History of residence in a congregate setting (eg, jail or prison, homeless shelter, or chronic care facility) or healthcare workers with unprotected exposure to subjects who are at high risk of TB
    - (ii) Close contact (ie, share the same air space in a household or other enclosed environment for a prolonged period [days or weeks, not minutes or hours]) with a person with active pulmonary tuberculosis (TB) disease within the last 12 months;
  - (h) Amputation due to peripheral artery disease;
  - (i) Any other medical condition or clinically relevant abnormal findings in physical examination, laboratory results, or electrocardiogram (ECG) during screening that, in the opinion of the investigator, may compromise the safety of the subject in the

study, reduce the subject's ability to participate in the study, or interfere with evaluation of MEDI3506.

- 10 Vaccinations
  - (a) Live or attenuated virus vaccination within 28 days of Visit 3 until the end of the follow-up period is not allowed.
  - (b) Vaccination against COVID-19 (either first or subsequent dose) within 28 days before Visit 3; for details, see Section 4.7.4.
- 11 Allergic reactions
  - (a) History of severe allergic reaction requiring hospitalization;
  - (b) History of severe reaction to any medication including biologic agents or human gamma globulin therapy;
  - (c) History of allergy or reaction to any component of MEDI3506 or dapagliflozin formulation.
- 12 Subjects with a known positive diagnostic nucleic acid or antigen test for SARS-CoV-2 within 6 weeks prior to randomization visit. a
- 13 Subjects with a significant COVID-19 illness within 6 months of randomization:
  - (a) Subjects with a diagnosis of COVID-19 pneumonia based on radiological assessment;
  - (b) Subjects with diagnosis of COVID-19 with significant findings from pulmonary imaging tests;
  - (c) Subjects with a diagnosis of COVID-19 requiring hospitalization and/or oxygen supplementation therapy.
- 14 Receiving any of the prohibited concomitant medications (see Section 4.7.2) including:
  - (a) Renin inhibitor or an aldosterone antagonist when used in combination with an ACEi or an ARB within 2 months of Visit 1;
  - (b) Ongoing use of any biologic drug and/or small molecule targeting the immune system (eg, TNF blockers, anakinra, rituximab, abatacept, tocilizumab, cyclophosphamide, cyclosporine, tacrolimus, mycophenolate mofetil, or corticosteroids other than topical or inhaled);
  - (c) Subjects on serum creatinine-altering drugs should be on long-term treatment at a stable dose prior to study entry. Drugs considered serum-altering include but are not limited to amphotericin, cimetidine, clofibrate, dronedarone, ketoconazole, probenecid, ranolazine, trimethoprim, aminoglycosides, or cephalosporins. Generally, any drug that has a putative  $\geq 5\%$  effect on serum creatinine is considered serum creatinine-altering. The following exclusion criteria apply:
    - (i) New treatment or change of dose within 6 weeks prior to Visit 1
    - (ii) Expected change of dosing regimen during the study
    - (iii) Minor ACEi or ARB dose adjustment within 2 weeks of Visit 1 is acceptable, but any dose adjustments during the course of the study (ie, for control of hyperkalemia) should be discussed with the sponsor/ medical monitor
    - (iv) Clinically indicated short-term use of serum creatinine-altering drugs to treat acute conditions during the study may be allowed.

- 15 Donation of blood or significant blood loss
  - (a) All sites except Japan: Donation of blood or significant blood loss in excess of 500 mL within 3 months prior to Visit 3 (or > 1200 mL in the year prior to Visit 3).
  - (b) For Japan only:
    - (i) For male subjects, donation of whole blood or significant blood loss in excess of 400 mL within 3 months prior to Visit 3 or > 1200 mL in the year prior to Visit 3.
    - (ii) For female subjects, donation of whole blood or significant blood loss in excess of 400 mL within 4 months prior to Visit 3 or > 800 mL in the year prior to Visit 3.
- 16 Plasma donation within 60 days prior to Visit 3.
- 17 Subjects who are institutionalized.
- 18 An employee, or close relative of an employee, of AstraZeneca, the contract research organization, or the study site, regardless of the employee's role.
- 19 Pregnancy or intention to become pregnant during the course of the study, breastfeeding, or unwillingness to use a highly effective method of contraception throughout the study in female subjects of childbearing potential.

a Investigators should use their best clinical judgement to decide on measures needed to minimize the risk of randomizing patients with an active SARS-CoV-2 infection. To do so, they should consider the local status of the COVID-19 pandemic, the subject's medical and vaccination history, local recommendations regarding outpatient COVID-19 screening, and testing policies.

#### **4.1.4 Subject Enrollment and Randomization**

Study participation begins (ie, a subject is "enrolled") once written informed consent is obtained. Once informed consent is obtained, a subject identification (SID) number will be assigned by a central system (eg, an interactive voice/web response system [IXRS]), and the screening evaluations may begin to assess study eligibility (inclusion/exclusion) criteria. The SID number will be used to identify the subject during the screening process and throughout study participation, if applicable.

A master log of all consented subjects will be maintained at the site and will document all screening failures (ie, subjects who are consented but do not meet study eligibility criteria and/or are not randomized), including the reason(s) for screening failure.

Subjects who fail to meet the inclusion/exclusion criteria may be rescreened any time during the recruitment period and receive a new SID number. Subjects can be rescreened up to 2 times. Prior to rescreening, subjects must be reconsented and receive a new SID number. Subjects who have been discontinued from treatment will not be rescreened.

Where subjects who do not meet the inclusion and/or exclusion criteria are randomized in error, or incorrectly started on treatment, or where subjects subsequently fail to meet the study

criteria post initiation, the investigator should inform the medical monitor immediately. The investigator and/or medical monitor may determine that the incorrectly randomized subject will not receive any further investigational product if the inclusion/exclusion criteria violation would put the subject at undue risk.

#### **4.1.5 Withdrawal from the Study**

Subjects are free to withdraw their consent to participate in the study (investigational product and assessments) at any time, without prejudice to further treatment. A subject who considers withdrawing from the study must be informed by the investigator about modified follow-up options (eg, telephone contact, a contact with a relative or treating physician, or information from medical records). Subjects who withdraw consent will be asked about the reason(s) and the presence of any AEs. If the subject is willing, the subject will be seen and assessed by the investigator.

AEs will be followed up; all study materials should be returned by the subject. If a subject withdraws from further participation in the study, then no further study visits or data collection should take place.

#### **4.1.6 Discontinuation of Investigational Product**

Subjects are free to discontinue study drugs at any time, without prejudice to further treatment.

- Subjects who choose to discontinue MEDI3506 prior to the dapagliflozin period (Day 85 to Day 168) will not proceed on dapagliflozin and are expected to attend their next scheduled study visit for an Early Discontinuation Visit (see Table 6) and then to complete the assessments per the follow-up visit described in Table 7. Visit 10/EOS will be conducted 60 days ( $\pm$  5 days) after the last visit performed.
- Subjects who choose to discontinue MEDI3506 during the dapagliflozin period (Day 85 to Day 168) prior to the end of the treatment period are expected to attend their next scheduled study visit for an Early Discontinuation Visit (see Table 6) and then to complete the assessments per the follow-up visit described in Table 7. Visit 10/EOS will be conducted 60 days ( $\pm$  5 days) after the last visit performed.
- Subjects who choose to discontinue dapagliflozin during the dapagliflozin period (Day 85 to Day 168) prior to the end of the treatment period are expected to continue in the study on remaining study therapy according to the schedule of study procedures for the remainder of the study.

An individual subject will not receive any further investigational product if any of the following occur in the subject in question:

- 1 Withdrawal of consent from further treatment with investigational product
- 2 Lost to follow-up

- 3 An AE that, in the opinion of the investigator or the sponsor, warrants discontinuation of further dosing or meets criteria for discontinuation from investigational product (including, but not limited to, anaphylactic reaction to investigational product, new onset or progression of heart failure).
- 4 After initial dosing, there exists a clinically significant safety issue based on information not known or not disclosed prior to randomization
- 5 Subject noncompliance that, in the opinion of the investigator or sponsor, warrants treatment discontinuation for safety reasons (eg, refusal or inability to adhere to scheduled visits)
- 6 Pregnancy

Appendix C describes actions required in cases of increases in liver biochemistry.

Consider temporary interruption of dapagliflozin if DKA is suspected. The subject should be promptly evaluated. If DKA is confirmed, dapagliflozin should be discontinued permanently.

Subjects who have a positive SARS-CoV-2 nucleic acid test should be immediately evaluated by the investigator and sponsor. Based on investigator and sponsor judgement, subjects may be temporarily or permanently discontinued from treatment.

Subjects who are permanently discontinued from receiving investigational product will be followed for protocol-specified assessments including follow-up of any AEs unless consent is withdrawn from further study participation (Section 4.1.5), the subject is lost to follow-up, or the subject is enrolled in another clinical study.

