### **1.7.2 Dapagliflozin**

The safety profile of dapagliflozin has been evaluated in clinical development programs for T2DM, T1DM, heart failure and CKD. This includes more than 15,000 subjects treated with

dapagliflozin for T2DM, more than 1,000 subjects treated with dapagliflozin for T1DM, more than 1,400 subjects treated with dapagliflozin for DKD, and more than 2,000 subjects treated with dapagliflozin for heart failure. Overall, treatment with dapagliflozin 5 mg was similar to treatment with dapagliflozin 10 mg in both T1DM and T2DM. The safety profile of dapagliflozin was overall consistent across the studied indications.

The most commonly reported AEs associated with the use of dapagliflozin include genital infections, urinary tract infections, back pain, and polyuria. In addition, rash has been identified as an AE of unknown frequency in marketed use of dapagliflozin.

In the cardiovascular outcomes study, dapagliflozin on the Incidence of Cardiovascular Events (DECLARE), 8,574 patients received dapagliflozin 10 mg and 8,569 patients received placebo for a median exposure time of 48 months. Events of diabetic ketoacidosis (DKA) were reported in 27 patients in the dapagliflozin 10 mg group and 12 patients in the placebo group. The events occurred evenly distributed over the study period. Of the 27 patients with DKA events in the dapagliflozin group, 22 had concomitant insulin treatment at the time of the event.

The DAPA-CKD renal outcome study has shown 10 mg dapagliflozin to be efficacious and well tolerated in a wide range of patients with CKD (2152 patients treated with dapagliflozin; median follow-up = 2.4 years) (Heerspink et al, 2020a). In patients with an estimated glomerular filtration rate (eGFR) 25 to 75 mL/min/1.73m^2 dapagliflozin was shown to significantly reduce the combined risk of: 1) sustained decline in eGFR of at least 50%; 2) end-stage kidney disease; 3) or death from renal or cardiovascular causes (Heerspink et al, 2020a).

Taken together, SGLT2i have been shown to consistently reduce the risk of clinically important, patient-level cardiovascular outcomes and emerging data suggest that the combination of ACEi or ARB and SGLT2i should be routinely offered to patients with T2DM who have, or are at high risk of, progressive kidney disease (de Boer et al, 2020).

More detailed information about the known and expected benefits and potential risks of dapagliflozin may be found in the respective current IB (Edition 17).

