## 4.2 Schedule of Study Procedures

Whenever vital signs, 12-lead ECGs, and blood draws are scheduled for the same nominal time, the blood draws should occur last. The timing of the first 2 assessments should be such that it allows the blood draw (eg, PK blood sample) to occur at the proper nominal time. Randomization should only proceed if all required assessments have been performed and all inclusion/exclusion criteria as well as other protocol restrictions have been evaluated; see Section 4.1.2, Section 4.1.3, and Section 4.7.

Dosing of subjects should only be carried out if all required assessments have been performed and evaluated. Dosing is not allowed to proceed until the investigator has determined that the results are within acceptable range according to the defined stopping criteria; see Section 4.1.6. Laboratory assessment results should also be reviewed at every visit to ensure that stopping criteria have not been met.

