In the event of treatment interruption of any duration, resuming administration of ACEi or ARB and dapagliflozin should be considered as early as possible. Careful consideration should be given to the individual risk/benefit profile and the subject's needs.

Dapagliflozin may decrease blood pressure. Adjust other antihypertensive therapies after the start of the study if needed.

Dapagliflozin is a mild diuretic. Adjust other diuretic therapies after the start of the study if needed.

Starting dapagliflozin may require a gradual dose reduction of insulin and/or insulin secretagogues (sulfonylureas, meglitinides) to avoid hypoglycemia (Garber et al, 2020).

Treatment with dapagliflozin should be stopped immediately if diabetic ketoacidosis is suspected or confirmed, and treatment should not be re-started unless another clear precipitating factor for the condition is identified and resolved (AstraZeneca, 2020).

For more details, refer to the dapagliflozin drug label.

Modest hyperkalemia should generally be managed, if possible, without reducing or discontinuing ACEi or ARB, unless there is another reason to do so (Kidney Disease: Improving Global Outcomes Diabetes Work, 2020).

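### Sections 4.1.6 and 4.7.3 give different dapagliflozin rules for suspected and for confirmed diabetic ketoacidosis, and nothing says which one governs

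*Protocol*

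**What the plan says.** Section 4.1.6 (Discontinuation of Investigational Product) treats suspected and confirmed DKA separately.

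- Suspected: "Consider temporary interruption of dapagliflozin if DKA is suspected", followed by "The subject should be promptly evaluated".
- Confirmed: "If DKA is confirmed, dapagliflozin should be discontinued permanently".

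Section 4.7.3 (Considerations for SGLT2i and RAASi) covers both states in one sentence. It begins "Treatment with dapagliflozin should be stopped immediately if diabetic ketoacidosis is suspected or confirmed" and goes on to say that "treatment should not be re-started unless another clear precipitating factor for the condition is identified and resolved".

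Section 4.2 makes a general reference to Section 4.1.6: before dosing, the investigator must have determined that "the results are within acceptable range according to the defined stopping criteria; see Section 4.1.6".

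Dapagliflozin 10 mg daily is part of the protocol treatment from Day 85 to Day 168. On background risk, Section 1.7.2 cites a cardiovascular outcomes study in which "8,574 patients received dapagliflozin 10 mg and 8,569 patients received placebo for a median exposure time of 48 months". It reports: "Events of diabetic ketoacidosis (DKA) were reported in 27 patients in the dapagliflozin 10 mg group and 12 patients in the placebo group".

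**The concern.** The two sections differ at both steps, in opposite directions. On suspicion, Section 4.1.6 leaves interruption to judgement and Section 4.7.3 asks for an immediate stop. On confirmation, Section 4.1.6 ends dapagliflozin for good and Section 4.7.3 leaves a conditional way back.

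A site working only from Section 4.1.6 could let a subject keep taking tablets while a suspected case is evaluated. A site working only from Section 4.7.3 could restart the drug after a confirmed case once a precipitant had been resolved. Each would be following the protocol as it read it, and departing from it elsewhere. With around 130 sites planned (Section 3.1.1), uniform handling cannot be assumed.

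The stake is subject safety and consistent conduct during the dapagliflozin period.

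**Working it through.** **The two rules side by side**

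| Situation | Section 4.1.6 | Section 4.7.3 | Stricter |
|---|---|---|---|
| DKA suspected | Consider a temporary interruption; evaluate promptly | Stop at once | 4.7.3 |
| DKA confirmed | Discontinue permanently, no exception given | Stop at once; restart possible if another clear precipitant is found and resolved | 4.1.6 |

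Both are current body text. The change log suggests how they diverged: the DKA criteria entered Section 4.1.6 with Amendment 2 (Section 9.4, item 37), and the SGLT2i treatment guidance entered Section 4.7.3 with Amendment 3 (Section 9.3, item 27).

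**Does any cross-reference settle it?**

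- Section 4.2 refers to Section 4.1.6 for stopping criteria when results are reviewed before dosing. It does not mention DKA.
- Section 4.2.3 refers to Section 4.1.6 only for follow-up after discontinuation.
- Section 4.1.6.1 refers the other way, to Section 4.7.3, for missed dapagliflozin doses.

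None ranks one section above the other. Letting either prevail would leave the weaker rule in force at one step.

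**How many confirmed cases might arise?** The protocol states no figure, so this is an illustration from its own inputs.

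*Inputs*
- Section 1.7.2: 27 of 8,574 patients on dapagliflozin and 12 of 8,569 on placebo had DKA; median exposure 48 months, taken as a mean of 4 years.
- Section 4.8.2: 565 randomized; evaluable 3 × 85 + 2 × 125 = 505.
- Section 3.1.2: Day 85 to Day 168 is 84 days.

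*Formulas*
- Rate = patients with DKA / (patients × 4 years)
- Person-years = subjects × 84 / 365.25
- Expected cases E = rate × person-years
- Chance of at least one (Poisson) = 1 − exp(−E)

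*Rates*
- Dapagliflozin: 27 / (8,574 × 4) = 0.787 per 1,000 person-years
- Placebo: 12 / (8,569 × 4) = 0.350 per 1,000 person-years

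*Exposure*
- 565 × 84 / 365.25 = 129.9 person-years
- 505 × 84 / 365.25 = 116.1 person-years

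| Rate used | Subjects | Expected cases | Chance of at least one |
|---|---|---|---|
| Dapagliflozin | 565 | 0.102 | 0.097 |
| Dapagliflozin | 505 | 0.091 | 0.087 |
| Placebo | 565 | 0.045 | 0.044 |
| Placebo | 505 | 0.041 | 0.040 |

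**The case against.** **The rules can be reconciled.** Stopping at once on suspicion is compatible with being told to consider interruption. Never restarting after confirmation satisfies Section 4.7.3, which limits restart and nowhere directs it. This is true, so the two texts are not commands that cannot both be met. But it works only if the site reads both sections and takes the stricter rule each time, which the protocol does not ask for. Section 4.7.3 also leans the other way: it treats permanent discontinuation of dapagliflozin as a last resort and favours early resumption after an interruption.

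**The specific rule controls.** Section 4.1.6 has a rule just for confirmed DKA, so the restart clause in Section 4.7.3 could be read as applying to suspected cases only. That reading is possible, and it makes the mismatch on suspicion the clearer of the two. It is not the natural one, because the restart clause sits in the sentence that names both suspected and confirmed DKA.

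**Sites have other safeguards.** Section 4.1.6 asks for prompt evaluation and lets the investigator or sponsor stop dosing for any adverse event that warrants it. Section 4.7.3 refers readers to the drug label for further detail. The first two do limit the risk. The label is not available here, and the reference to it does not say which protocol rule governs.

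**The numbers are very small.** This stands. The 0.10 counts all confirmed cases. The restart difference bites only in those with a resolved precipitant and dosing days left before Day 168.

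**Conclusion.** The inconsistency is real and sits in operative text at both steps. It is minor. Two current instructions for a serious event differ, and following one section alone can mean departing from the other.

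The illustrative range is 0.04 to 0.10 expected confirmed cases, with a 4% to 10% chance of at least one. It assumes that the cited study's rates carry over to this population, that its median exposure can stand for the mean, that each affected patient has one event, and that every counted subject takes dapagliflozin for the full 84 days. The figure of 565 overstates exposure, because subjects who stop MEDI3506 before Day 85 do not start dapagliflozin, nor do those who completed 12 weeks before Amendment 2. The rate in subjects with diabetic kidney disease could, on the other hand, be higher than in the cited study. Suspected cases later ruled out are not counted; they would fall under the suspicion rule, and the protocol gives no basis for a number.

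No effect on power, the primary analysis or its interpretation is claimed.

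**What to change.** State one rule in Section 4.1.6 and replace the DKA sentence in Section 4.7.3 with a cross-reference to it:

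- stop dapagliflozin immediately if DKA is suspected, and evaluate promptly;
- resume only if DKA is ruled out;
- discontinue permanently if DKA is confirmed.

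Whether restart after a confirmed case should ever be allowed is a clinical choice. If the sponsor's safety physicians prefer the restart condition now in Section 4.7.3, the same condition should appear in both sections. The essential point is a single wording.

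The cost is one paragraph in an amendment, plus a letter to sites if dosing is still under way. The stricter rule may slightly reduce dapagliflozin exposure in a few subjects. Design, sample size and analysis do not change.
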